|----------------------------|---|

| | |
|--|---|
| | 
9) Any previous medically adverse reaction to opioids or lemborexant:
 
10) Significant current suicidal or homicidal ideation (C-SSRS “yes” answers on questions 4 or 5) or a history of suicide attempt within the past 6 months.
 
11) Subjects with Suicidal Behaviors Questionnaire-Revised score ≥8 at the screening visit.
 
12) Any other severe acute or chronic medical or psychiatric condition or laboratory abnormality that may increase the risk associated with study participation or investigational product administration or may interfere with the interpretation of study results and, in the judgment of the investigator, would make the subject inappropriate for entry into this study.
 |
| TEST PRODUCT, DOSE, AND ROUTE OF ADMINISTRATION | 
Lemborexant 5 mg, 10 mg
 
Product will be administered orally once on each laboratory day in the clinical research unit (CRU) only.
 |
| CONTROL PRODUCT, DOSE AND ROUTE OF ADMINISTRATION | 
Placebo
 
Subjects who are randomized to placebo will receive identical capsules to the test product at the same time administered orally.
 |
| DURATION OF SUBJECT PARTICIPATION AND DURATION OF STUDY | 
Subjects will be on study for up to approximately 60 days (including intervening weekends)
 
Screening: up to approximately 30 days
 
Baseline: 1 day
 
Treatment : 6 days
 
Follow-up: 8 days
 
Note: Safety/PK Testing Weeks may be separated by up to approximately 14 days in order to better accommodate participant schedules.
 
The total duration of the study is expected to be 18 months.
 |

| | |
|--------------------------|---|

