| STATISTICS Primary Analysis Plan | 
Initial analyses will evaluate group differences on demographic and baseline variables, will use contingency tables with chi-square testing, ANOVA's, and examination of correlations between baseline variables, subjective responses, and clinical results. General data analysis procedures: Prior to data analysis procedures, groups will be examined for differences in baseline characteristics that could potentially influence treatment outcome. Any variables that differ between groups and are related to outcome measures will be examined as potential covariates in subsequent data analyses.
 
Primary outcome measures:
 
 1. Safety: Heart rate (HR), blood pressure (BP), respiratory rate, agitation and sedation (Richmond Agitation-Sedation Scale) and pulse oximetry during a placebo dose will be compared to HR and BP during each lemborexant dose (5 mg and 10mg doses). Changes in safety measures induced by lemborexant dose along with buprenorphine will be compared to those without lemborexant, by lemborexant dose level (5 mg and 10 mg doses), using a generalized linear mixed model analysis with the participant as a random effect for each outcome. Adverse event data will be compiled for lemborexant and placebo cohorts and presented as summary statistics. 2. Buprenorphine PK: Plasma concentration-time profiles of buprenorphine and its metabolite norbuprenorphine after doses during the lemborexant placebo/administration (Day 0,1, 2) will be analyzed to obtain pharmacokinetic parameter estimates of buprenorphine (Cmax, Tmax, AUC, apparent t½, CL/F for parent buprenorphine and metabolic (AUC) ratios for metabolites) by individual. These parameters will be compared within subjects on sessions with lemborexant. 3. Changes in secondary outcome and exploratory outcome measures induced by lemborexant dose along with buprenorphine will be compared to those without lemborexant, by lemborexant dose level (5 mg and 10 mg doses), using a generalized linear mixed model analysis with the participant as a random effect for each outcome. |

| | |
|----------------------------------|---|
| RATIONALE FOR NUMBER OF SUBJECTS | Projected sample size is 18 subjects who have completed at least one drug-drug interaction treatment session with primary endpoint data— 12 lemborexant-treated subjects, 6 placebo treated subjects. Sample size was determined based on primary outcome safety and PK measures. |

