The orexin 1 receptor antagonist SB-334867 attenuated heroin SA in adult rats and diminished cue-induced, but not prime-induced, reinstatement of heroin-seeking behavior following extinction (Smith and Aston-Jones 2012). Also, orexin 2 receptor antagonists reduce heroin intake in long-access (12 h), but not short-access (2 h), SA paradigms (Schmeichel, Barbier et al. 2015). Orexin 1 receptor antagonists attenuate morphine withdrawal symptoms in rats (Azizi, Mirnajafi-Zadeh et al. 2010, Laorden, Ferenczi et al. 2012). Dual orexin antagonists seem to be particularly well suited to treating OUD. Han et al., (2020) reviewed all similar studies and found that there is evidence from multiple animal models of opioid addiction supporting the use of orexin 1 and 2 receptor antagonists to reduce addictive behaviors. Matzeau and Martin-Fardon et al., (2020) evaluated orexin 1 antagonist SB-334867 and TCSOX229 an orexin 2 receptor antagonist in rats with an oxycodone self-administration model showing that the orexin 1 receptor antagonist suppressed self-administration but not the orexin 2 receptor antagonist.

As a first step in evaluating the potential for use of the orexin 1 and 2 receptor antagonist lemborexant as an adjunctive treatment for opioid use disorder in patients in MAT with buprenorphine, we propose a phase 1b/2a drug-drug interaction study examining two doses of lemborexant as an add-on to buprenorphine-naloxone

with 18 participants (12 treated with lemborexant and 6 treated with placebo. The lemborexant group will have two lab sessions each; one with each dose of med). All participants will be currently stable in MAT treatment with buprenorphine and have symptoms of insomnia as measured by the Pittsburgh Sleep Quality Index. This is parallel groups ascending dose study.

Specific Aims:

Primary: Aim 1: To examine safety-tolerability and drug-drug interactions between lemborexant and buprenorphine-naloxone in participants with opioid use disorder and insomnia who are in MAT with buprenorphine-naloxone.

Secondary: Aim 2: To examine lemborexant for an early signal of efficacy (anticraving, anxiolysis, impulsivity, and reduced subjective withdrawal symptoms) in participants with opioid use disorder and insomnia who are in MAT with buprenorphine-naloxone.

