If subjects meet inclusion criteria, they will be admitted as research participants to the clinical research unit (CRU) for a total of up to 4 overnight stays across the two inpatient admission visits to maintain complete monitoring for adverse events. While in the hospital, subjects will undergo procedures as described below. Subjects will not be allowed to smoke cigarettes, as smoking is not allowed in the hospital or anywhere on the VCU campus. Subjects who are identified as current smokers will have the option to use a nicotine patch dosed based on the amount of daily cigarettes smoked. Subjects will not be allowed to leave the CRU nor receive visitors if they wish to remain in the study. Subjects who are unable to comply with these restrictions will be dropped from the study. Eligible subjects will be randomized to Group A –placebo only or Group B – lemborexant. Six subjects will be assigned to Group A (placebo) and 12 subjects will be assigned to Group B (active lemborexant).

Study Drug Dosage: 5 mg of lemborexant, and 10 mg of lemborexant, all subjects will receive a dose equivalent to their current prescribed dose of buprenorphine-naloxone sublingually as a film or tablet.

STUDY OUTCOME MEAURES

Primary outcome measures:

1. Safety: Heart rate (HR), blood pressure (BP), respiratory rate, agitation and sedation (Richmond Agitation-Sedation Scale), capnography (EtCO₂), and pulse oximetry during placebo administration will be compared to those same measures after lemborexant. Changes in safety measures induced by buprenorphine-naloxone dose along with lemborexant will be compared to those without lemborexant. Adverse event data will be compiled for lemborexant and placebo cohorts and presented as summary statistics.
2. Buprenorphine PK: Plasma concentration-time profiles of buprenorphine and its metabolite norbuprenorphine and after doses during the lemborexant placebo/administration (Day 0,1, 2) will be analyzed to obtain pharmacokinetic parameter estimates of buprenorphine (C_{max}, T_{max}, AUC, apparent t_{1/2}, CL/F for parent buprenorphine and metabolic (AUC) ratios for metabolites) by individual. In addition lemborexant and its main metabolite M10 will be determined after each dose of buprenorphine and compared with published lemborexant PK parameters.

Secondary Outcome Measures:

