1. Subjective effects on opioid craving and anxiety as measured by a visual analog scale, and brief substance craving scale, and opioid withdrawal based on the Subjective Opioid Withdrawal Scale.
2. Objective opioid withdrawal based on the Clinical Opioid Withdrawal Scale.
3. Impulsivity as measured by delayed discounting. All measures will be compared between subjects receiving lemborexant versus those on placebo to determine the extent to which this measure is modified by the administration of lemborexant with buprenorphine vs. placebo with buprenorphine.

Exploratory Outcome Measures:

1. Pupillometry is used to measure change in pupil size as an indicator of lemborexant changes in buprenorphine central nervous system mu-opioid pharmacological effects (Rollins, Feiner et al. 2014). Single pupil measurements at scheduled times will be performed using a pupillometer per manufacturer's specification. The light in the measurement room will be maintained at 3.6 to 4.3 lux, using a Lutron light meter. Participants will be allowed to adjust to the room lighting for at least 3 minutes prior to any measurement. Pupillometry will be measured using the right eye for all participants, unless otherwise determined by the Investigator. The same eye will be used for all measurements in the study.
2. Sleep quality as measured by sleep diary and Pittsburgh Sleep Quality Index.
3. Relationship between baseline behavioral profiles as determined by the NIDA Phenotyping Battery and subjective response to lemborexant.

STUDY DRUG AND DOSAGE

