On PK/Safety Testing week 1 Study Day 2 lemborexant (or matching placebo) is given as 5 mg at 7:00 AM after an overnight stay on the CRU. On PK/Safety Testing Week 2 Study Day lemborexant (or matching placebo) is given as 10 mg at 7:00 AM. Subjects will be continuously monitored on the CRU for 8 hours after the lemborexant dose, which is past the C_{max} lemborexant concentration, which will occur between 8:00 AM and 10:00 AM. Blood samples for determination of buprenorphine concentration and its major metabolite norbuprenorphine and lemborexant and its major metabolite M10 will be collected pre-dose and specified timepoints during the hospital stay (Table 3). Plasma levels will be utilized to determine AUC (area under the concentration–time curve from Time 0 post-dose to infinity) and $T_{1/2}$ (apparent terminal half-life) using noncompartmental analysis, and C_{max} (maximum concentration), C_{24} (concentration at 24 hours post-dose), and T_{max} (time to C_{max}). Plasma buprenorphine and norbuprenorphine and lemborexant and M10 levels will be determined in the VCU Department of Pharmacology and Toxicology drug analysis laboratory.

Dispensing: Study drug will be dispensed by the research pharmacist and administered by the research nurse on the CRU.

Supply of Study Drug at the Site: Study drug will be provided to the CRU after an order from the study physician or nurse practitioner. Storage: At the testing facility, all lemborexant, buprenorphine, and placebo must be kept in a secure, locked storage place with access limited to authorized study personnel only.

Study Drug Accountability: All study medication will be administered on the CRU. The study staff will record an accurate accounting of each medication administered.

STUDY PROCEDURES AND GUIDELINES

A Schedule of Events representing the required testing procedures to be performed for the duration of the study is diagrammed in Tables 1-2. Prior to conducting any study-related activities, written informed consent and the Health Insurance Portability and Accountability Act (HIPAA) authorization must be signed and dated by the subject. In order to better accommodate participant schedules, PK/Safety Testing Weeks 1 and 2 may be separated by up to approximately 14 days.

Clinical Assessments:**Concomitant Medications**

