(Week 2 Days 1-6 are essentially identical to Week 1 Days 1-6, and the screening measures are only obtained once in the beginning).

TABLE 2: Schedule of Procedures and Assessments:

| Study Day | Screening & PhAB -30 to 0 (approx.) | Baseline Day 0 | PK/Safety Week 1 Study Days 1 & Week 2 Study Days 1 | PK/Safety Week 1 Study Day 2 & Week 2 Study Day 2 | PK/Safety Week 1 Study Day 3 & Week 2 Study Day 3 | PK/Safety Week 1 Study Day 4-7 & Week 2 Study Day 4-7 |
|--|-------------------------------------|----------------|---|--|---|---|
| Location | CARI/ MOTIVATE | CRSU | CRSU | CRSU | CRSU if needed, CARI/Motivate otherwise | CARI/ MOTIVATE |
| Procedure | | | | | | |
| Informed Consent | X | | | | | |
| Serum Chemistry | X | | | | | |
| Serum Hematology | X | | | | | |
| Admission to Unit | | X | X | | | |
| Discharge from Unit | | X | | X (if medically stable without motor and cognitive impairment) | X | |
| History, Physical Exam, and Neurological Exam | X | X | X | | | |
| Urine Pregnancy test (females) | X | X | X | X | | X |
| Psychiatric Interview (MINI) | X | | | | | |
| PhAB assessment battery and platform instruments | X | | | | | |
| Addiction Severity Index (ASI-lite) | X | | | | | |
| Brief Substance Craving Scale | X | X | X | X | X | X |

| Study Day | Screening & PhAB -30 to 0 (approx.) | Baseline Day 0 | PK/Safety Week 1 Study Days 1 & PK/Safety Week 2 Study Days 1 | PK/Safety Week 1 Study Day 2 & PK/Safety Week 2 Study Day 2 | PK/Safety Week 1 Study Day 3 & PK/Safety Week 2 Study Day 3 | PK/Safety Week 1 Study Day 4-7 & PK/Safety Week 2 Study Day 4-7 |
|--|-------------------------------------|----------------|---|---|---|---|
| Timeline Follow Back Drug Use | X | X | X | | | X |
| Drug Use History | X | | | | | |
| Concomitant Medications | X | X | X | | | X |
| Clinical Opiate Withdrawal Scale (COWS) | X | X | X | X | X | X |
| Subjective Opiate Withdrawal Scale (SOWS) | X | X | X | X | X | X |
| Urine drug screen | X | X | X | X | X | X |
| Breathalyzer or Salivary Alcohol Level | X | X | X | X | X | X |
| Verify Inclusion & Exclusion | X | X | X | | | |
| Vital Signs | X | X | X | X | X | X |
| 12-Lead ECG (baseline triplicate) and singlet thereafter) | X | X | X | X | X | |
| Brief Physical Exam | X | | | X | X | X |
| Continuous pulse oximetry, capnography, and physiological monitoring | | X | | X | | |
| Pupil Measurement | | X | | X | | |
| Adverse Events Inventory | | X | X | X | X | X |

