mg doses), using a generalized linear mixed model analysis with the participant as a random effect for each outcome. Adverse event data will be compiled for lemborexant and placebo cohorts and presented as summary statistics.

2. Buprenorphine PK: Plasma concentration-time profiles of buprenorphine and its metabolite norbuprenorphine after doses during the lemborexant placebo/administration (Day 0, 1, 2) will be analyzed to obtain pharmacokinetic parameter estimates of buprenorphine (Cmax, Tmax, AUC, apparent t_{1/2}, CL/F for parent buprenorphine and metabolic (AUC) ratios for metabolites) by individual. These parameters will be compared within subjects on sessions with lemborexant. Lemborexant PK will be compared with published lemborexant PK data. As it would be unethical to withhold buprenorphine treatment from patients who are on buprenorphine for MAT, there will be no lemborexant dose without buprenorphine.

3. Changes in secondary outcome measures induced by lemborexant dose along with buprenorphine will be compared to those without lemborexant, by lemborexant dose level (5 mg and 10 mg doses), using a generalized linear mixed model analysis with the participant as a random effect for each outcome.

Safety and tolerability data will be summarized by treatment group.

Adverse event rates will be coded by body system and MedDra classification term. Adverse events will be tabulated by treatment group and will include the number of patients for whom the event occurred, the rate of occurrence, and the severity and relationship to study drug.

Interim Analysis

There will be no formal interim analysis.

Rationale for sample size: Sample size for effect of lemborexant on recommendations from the FDA regarding phase I safety studies.

DATA COLLECTION, RETENTION AND MONITORING

Data Collection Instruments

The Investigator will prepare and maintain adequate and accurate source documents designed to record all observations and other pertinent data for each subject treated with the study drug.

Study personnel at each site will enter data from source documents corresponding to a subject's visit into the protocol-specific paper/electronic CRF when the information corresponding to that visit is available. Subjects will not be identified by name in the study database or on any study documents to be collected by the Sponsor (or designee), but will be identified by a subject number.

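### The mixed models name only a participant random effect although dose varies by session, so outcomes read several times per session would get standard errors that are too small for within-participant dose contrasts

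*Combined protocol and SAP*

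**What the plan says.** Statistical Methods and Considerations, items 1 and 3, and the Statistics row of the synopsis give one model for the safety and the secondary outcomes: changes with lemborexant are compared with those without it, by dose level, "using a generalized linear mixed model analysis with the participant as a random effect for each outcome". The synopsis also covers exploratory measures: "Changes in secondary outcome and exploratory outcome measures induced by lemborexant dose along with buprenorphine will be compared to those without lemborexant". The main statistical section names only secondary measures in item 3. Neither place names a session term, a residual correlation structure, a time term or a degrees-of-freedom method.

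Dose is fixed within a session. According to the synopsis, "Product will be administered orally once on each laboratory day", and the Background adds: "The lemborexant group will have two lab sessions each; one with each dose of med". Day 0 is a further session, without lemborexant.

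Readings within a session differ by outcome:

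- Table 2 lists "Continuous pulse oximetry, capnography, and physiological monitoring" on Day 0 and on Day 2 of each testing week. Study Drug and Dosage says "Subjects will be continuously monitored on the CRU for 8 hours after the lemborexant dose".
- For pupil size, Study Outcome Measures says: "Single pupil measurements at scheduled times will be performed". The times are not given.
- Visual analog scales are collected in each administration session, without a stated number of readings.
- Vital signs are listed per study day, without times. The sedation, withdrawal, craving and discounting measures have bare marks in Table 2.

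**The concern.** A participant intercept makes all readings from one person equally alike, whichever session they come from. Readings from one afternoon usually resemble each other more than readings taken a week apart, because sleep, other drug use, probe placement and unit conditions change from day to day. A participant-only model puts that day-to-day variation into the residual and then divides it by the number of readings. Dose changes only between sessions, so the day-to-day variation is the error that matters for comparing doses within a person, and averaging more readings does not remove it. A fixed week term does not help, because the variation differs from person to person.

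The contrast at risk is one the plan names: change in safety measures with lemborexant against without it, by dose level. Too small a standard error could turn ordinary day-to-day variation into an apparent lemborexant effect. The first hypothesis is that safety measures are not altered, so an interval offered in support of it would also be too narrow.

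**Working it through.** **Figures in the plan.** There are 12 lemborexant and 6 placebo participants (12 + 6 = 18) and three sessions each (Day 0 and two dosing sessions). The plan states no alpha, power, effect size, SD or variance component, so there is no figure of its own to reproduce.

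**Assumed.** Two-sided 5% tests; *m* readings per session entering the model; ρ, the session-to-session share of the within-participant variance (set to 1). Neither *m* nor ρ is in the documents, so ranges are shown.

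**Step 1: true variance.** The mean of *m* readings from one session has within-participant variance L/*m*, with L = 1 + (*m* − 1)ρ.

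**Step 2: variance the model uses.** With fixed group-by-session means and a participant intercept, the residual pools two sources:

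- participant-by-session variation, on (12 − 1)(3 − 1) + (6 − 1)(3 − 1) = 32 degrees of freedom, with expected mean square L
- variation between readings within a session, on 18 × 3 × (*m* − 1) = 54(*m* − 1) degrees of freedom, with expected mean square 1 − ρ

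So s² = [32L + 54(*m* − 1)(1 − ρ)] / [32 + 54(*m* − 1)].

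**Step 3: ratio and rejection rate.** True SE / model SE is k = √(L/s²). The false rejection rate is approximately 2[1 − Φ(1.96/k)].

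**Example, *m* = 8 and ρ = 0.2.** L = 1 + 7 × 0.2 = 2.4. s² = (32 × 2.4 + 378 × 0.8)/410 = 379.2/410 = 0.925. k = √(2.4/0.925) = 1.61. 1.96/1.61 = 1.22, so the test rejects about 22% of the time.

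| ρ | *m* = 4: k | *m* = 4: rejects | *m* = 8: k | *m* = 8: rejects |
|---|---|---|---|---|
| 0 | 1.00 | 5% | 1.00 | 5% |
| 0.05 | 1.08 | 7.0% | 1.17 | 9.5% |
| 0.1 | 1.16 | 9.1% | 1.33 | 14.0% |
| 0.2 | 1.31 | 13.5% | 1.61 | 22.4% |
| 0.4 | 1.60 | 21.9% | 2.11 | 35.4% |

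With *m* = 1, L = s² = 1, so k = 1 and the rate is 5%.

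**Check by simulation.** Null trials of this design (4,000 per cell) gave the following:

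- Change from Day 0 to the 10 mg session against the placebo change: 6.7% to 21.6% for *m* = 4 and 8.9% to 34.3% for *m* = 8, over ρ = 0.05 to 0.4. The 10 mg versus 5 mg contrast behaves the same way.
- Few readings: 8% at *m* = 2, ρ = 0.2.
- Serial correlation alone, *m* = 8: 13% at lag-one correlation 0.3 and 28% at 0.6.
- Same contrasts with participant-by-session variation as the error term: 4% to 6% throughout.
- Lemborexant versus placebo in the same session, participant intercept only: 4% to 7%.

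A smaller check (200 trials per cell) fitted a full mixed model with dose and session as fixed factors. At ρ = 0.2 it rejected 15% against 5.5% with a session component for *m* = 8, and 16% against 6.5% for *m* = 4. The 15% is below the table's 22%, with a Monte Carlo error of √(0.15 × 0.85/200) = 2.5 points. That model has no group term, so it also draws on between-participant information. The direction is the same.

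**The case against.** A reader might infer that the plan prescribes a wrong model throughout, so that every safety and secondary result has a standard error far too small. The documents do not support this, for four reasons.

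- The plan says the participant is a random effect. It does not say that it is the only one, nor whether raw readings, changes or one summary per session are modelled. Continuous bedside monitoring does not mean that every monitored value enters the model.
- Several outcomes may have one value per session. The craving scale covers a 24-hour period, and vital signs are listed by study day. With one value per session there is no inflation.
- The randomised comparison with placebo in the same session is nearly unaffected, because the participant intercept covers most of its error. Simulated rates are 4% to 9%, depending on the reference distribution and the assumptions. The plan does not explicitly call for a 10 mg versus 5 mg test.
- Rates well above the table's need many strongly correlated readings, such as 47% with 14 readings at ρ = 0.4. Nothing in the documents fixes those values.

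Buprenorphine pharmacokinetics are reduced to parameters per individual and do not use this model. Adverse events are descriptive, and the plan sets no equivalence margin.

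All of this stands and limits the point. It does not remove it. Besides the continuous monitoring, the study overview promises to characterise onset, duration and size of effect, which one value per session cannot show. The individual stopping criteria ask whether heart rate, blood pressure, oximetry and respiratory rate recover within about 30 minutes, which requires repeated readings when a limit is crossed. The plan states a reduction to one set of values per session for pharmacokinetics and none for safety.

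**Conclusion.** The point holds conditionally. If repeated readings within a session are modelled with a participant intercept alone, contrasts between a lemborexant session and Day 0, and between the two doses if tested, are anticonservative. With ρ from 0.05 to 0.4, false rejection at a nominal 5% is about 7% to 22% with 4 readings and about 9% to 35% with 8. The true standard error is then 1.08 to 1.60 and 1.17 to 2.11 times the model's. These sizes rest on assumed *m*, ρ and alpha.

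The outcomes most exposed are pulse oximetry, capnography and other monitored vital measures, followed by pupil size and the visual analog scales if they are read more than once per session. Outcomes with one value per session, and the same-session comparison with placebo, give no material cause for concern. What the documents establish is an undefined unit of analysis and an incomplete random-effects structure. They do not establish that the final standard errors will be wrong.

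**What to change.** In the Statistics row of the synopsis and in items 1 and 3 of Statistical Methods and Considerations, state for each outcome the number and timing of readings per session and which of them enter the model. Then:

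- **Repeated readings:** either analyse one prespecified summary per participant and session, or keep the readings and add a participant-by-session random effect, with serial residual correlation where needed. Choose one per outcome in advance. The two agree for balanced Gaussian data but not in general for ordinal scores such as the agitation-sedation scale.
- **One value per session:** keep the participant random effect only. In a Gaussian model a participant-by-session effect could not be separated from the residual.
- **Gaussian models:** use Kenward-Roger or Satterthwaite degrees of freedom, since only 18 participants, 6 of them on placebo, carry the comparison.

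The cost is a few sentences or a short table, with no change to data collection. Intervals for within-participant contrasts of the repeated measures become wider, by roughly the ratios k shown above. The choice should be fixed before the blind is broken, so that the unit of analysis is not picked after the results are seen.
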